### **10.4.3 Concomitant Medications and Treatments**

Concomitant therapy includes any medications (*prescription drugs or over-the-counter drugs, herbal or homeopathic remedies, nutritional supplements*) used by a patient from 7 days before screening through the study completion visit.

All concomitant medications administered to the patient will be reported from 7 days before screening through 4 weeks following receipt of the last dose of study drug. The drug name, its route of administration, as well as its start and stop dates will be recorded.

*Any new anti-cancer therapies initiated within the safety follow-up visit (including drug name and date of initiation) will be recorded as well.*

#### **Use of Colony Stimulating Factors**

Primary prophylactic use of colony stimulating factors (CSF) is not permitted, but they may be used to treat treatment-emergent neutropenia as per current American Society of Clinical Oncology (ASCO) guidelines ([Smith et al. 2006](#)). If neutropenic complications are observed in a cycle in which primary prophylaxis with CSFs was not received, secondary prophylaxis may be given at the discretion of the investigator but only if dose reduction or delay are not considered a reasonable alternative.

#### **10.4.3.1 Drug Interactions of GDC-0810**

Nonclinical studies have shown that the major metabolic pathway of GDC-0810 was via glucuronidation by multiple UDP-glucuronosyltransferase (UGT) isoforms. GDC-0810 was shown to inhibit human CYP enzymes in vitro, especially CYP2B6 and CYP2C enzymes; therefore, drug-drug interactions with co-administered CYP2B6 and CYP2C substrates cannot be excluded and should be avoided. Note that many of these medications are metabolized by multiple CYP enzymes, thus attenuating the potential for drug-drug interactions to some extent. If there is clinical need for a particular CYP2B6 and CYP2C substrate drug, dose adjustments and/or use of alternative medications are recommended. A list of sensitive in vivo CYP2B6 and CYP2C substrates and substrates with narrow therapeutic range can be found in [Appendix 8a](#). GDC-0810 was also shown to inhibit human transporters in vitro, including OATP1B1/1B3. A drug-drug interaction study with pravastatin as the OATP1B1/1B3 substrate has been initiated to evaluate the potential risk. *The preliminary PK results showed no significant drug-drug interaction between GDC-0810 and pravastatin.*

#### **10.4.3.2 Drug Interactions of Palbociclib**

Palbociclib is primarily metabolized by CYP3A and sulfotransferase (SULT) enzyme SULT2A1. In vivo, palbociclib is a time-dependent inhibitor of CYP3A.

#### **10.4.3.3 Agents that may increase palbociclib plasma concentrations**

##### **Effect of CYP3A inhibitors**

Co-administration of a strong CYP3A inhibitor (itraconazole) increased the plasma exposure of palbociclib in healthy subjects by 87%. Avoid concomitant use of strong CYP3A inhibitors (e.g., clarithromycin, indinavir, itraconazole, ketoconazole, lopinavir/ritonavir, nefazodone, neflifavir, posaconazole, ritonavir, saquinavir, telaprevir, telithromycin, verapamil, and voriconazole). Avoid grapefruit or grapefruit juice during palbociclib treatment (Ibrance® Prescribing Information). If co-administration of palbociclib with a strong CYP3A inhibitor cannot be avoided, reduce the dose of palbociclib. A list of strong CYP3A inhibitors can be found in [Appendix 8b](#).

#### **10.4.3.4 Agents that may decrease palbociclib plasma concentrations**

##### **Effect of CYP3A inducers**

Co-administration of a strong CYP3A inducer (rifampin) decreased the plasma exposure of palbociclib in healthy subjects by 85% (Ibrance® Prescribing Information). Avoid concomitant use of strong CYP3A inducers (e.g., phenytoin, rifampin, carbamazepine and St. John's Wort). Co-administration of moderate CYP3A inducers may also decrease the plasma exposure of palbociclib. Avoid concomitant use of moderate CYP3A inducers (e.g., bosentan, efavirenz, etravirine, modafinil, and nafcillin). A list of strong and moderate CYP3A inducers can be found in [Appendix 8c](#).

#### **10.4.3.5 Drugs that may have their plasma concentrations altered by palbociclib**

Co-administration of midazolam with multiple doses of palbociclib increased the midazolam plasma exposure by 61%, in healthy subjects, compared with administration of midazolam alone. The dose of the sensitive CYP3A substrates with a narrow therapeutic index (e.g., alfentanil, cyclosporine, dihydroergotamine, ergotamine, everolimus, fentanyl, pimozide, quinidine, sirolimus and tacrolimus) may need to be reduced as may increase their exposure (Ibrance® Prescribing Information). A list of sensitive in vivo CYP3A substrates and CYP3A substrates with narrow therapeutic range can be found in [Appendix 8a](#).

#### **10.4.3.6 Drug Interactions of LHRH Agonists**

##### **Leuprolide acetate**

No pharmacokinetic-based drug-drug interaction studies have been conducted; however, drug interactions are not expected to occur.

##### **Goserelin acetate**

No formal drug-drug interaction studies have been performed. No confirmed interactions have been reported between goserelin acetate (Zoladex®) and other drugs.

##### **Triptorelin pamoate**

No drug-drug interaction studies involving triptorelin have been conducted.

## **Drug-Drug Interactions with GDC-0810 and Palbociclib**

Glucuronidation is the major metabolic pathway of GDC-0810. GDC-0810 is a weak inhibitor of CYP3A. Palbociclib is primarily metabolized by CYP3A and SULT2A1 and shown as a weak time-dependent inhibitor of CYP3A. In general, on the basis of data on GDC-0810 and palbociclib, the risk for drug interactions is low.

## **Drug-Drug Interactions with GDC-0810 and LHRH Agonists**

No pharmacokinetic-based drug-drug interaction studies have been conducted with LHRH agonists. However, because LHRH agonists are peptides that are primarily degraded by peptidase and not by cytochrome P-450 enzymes and glucuronidation, the risk for drug interactions is low.

## **Prohibited Therapies**

No other hormonal therapy, chemotherapy, immunotherapy, or experimental anti-cancer medications will be permitted while the patient is in the study.

## **Other Therapies**

Symptomatic anti-emetics, anti-diarrheal therapy, as well as other palliative and supportive care for disease- or treatment-related symptoms may be administered at the investigator's discretion. All concomitant medication and/or therapies should be documented in the patient's CRF. In certain instances, focal radiation therapy for palliation of bone disease-related symptoms might be allowable after discussion with the Sponsor; however, the need for radiation therapy will generally be considered indicative of progressive disease. Bone-sparing agents (e.g., bisphosphonates, denosumab) for palliation of bone metastases or for the treatment of osteoporosis/osteopenia are allowed in the study. In general, it is recommended to stop GDC-0810 and/or palbociclib treatment at least 7 days prior to surgical procedures. Postoperatively, the decision to reinitiate GDC-0810 and/or palbociclib treatment should be based upon a clinical assessment of satisfactory wound healing and recovery from surgery.

## **Lifestyle Guidelines**

Patients should take precautionary measures regarding sun exposure, with daily sunscreen use and wearing protective clothing, sunglasses, and hats when outdoors.

## **Dietary Restrictions**

Patients enrolled in Cohort C1 who are receiving GDC-0810 concurrently with palbociclib should avoid grapefruit and grapefruit juice due to the CYP3A inhibition.

## **10.5 STUDY DRUG ACCOUNTABILITY**

The Sponsor (or designee) will ship GDC-0810 to the investigational sites. The initial study drug shipment will be shipped after site activation (i.e., all required regulatory documentation has been received by the Sponsor and a contract has been executed). Study drug treatments, palbociclib and LHRH agonist will be prescribed by the study sites and cost of study treatment will be reimbursed by the Sponsor.

An accurate and current accounting of the dispensing and return of all applicable study drug (i.e. GDC-0810 and study drug treatment) for each patient will be maintained on an ongoing basis by a member of the study site staff. The number of study drug dispensed and returned by the patient will be recorded on the accountability log. The study monitor will verify these documents throughout the course of the study.

At the end of the study, the Sponsor will provide instructions as to the disposition of any unused study drug. If destruction at the site is authorized, the investigator must ensure that all investigational product is destroyed in compliance with the applicable environmental regulations, institutional policy, and any other special instructions provided by the Sponsor. Drug destruction must be adequately documented.

### **Post-Trial Access to GDC-0810**

The Sponsor (Genentech) is a member of the Roche group and is subject to Roche's global policies. The Sponsor will offer post-trial access to the study drug GDC-0810 free of charge to eligible patients in accordance with the Roche Global Policy on Continued Access to Investigational Medicinal Product, as outlined below. A patient will be eligible to receive study drug after the end of the study if all of the following conditions are met:

- The patient has a life-threatening or severe medical condition and requires continued study drug treatment for her well-being.
- There are no appropriate alternative treatments available to the patient.
- The patient and his or her doctor comply with and satisfy any legal or regulatory requirements that apply to them.

A patient will not be eligible to receive study drug after the end of the study if any of the following conditions are met:

- The study drug is commercially marketed in the patient's country and is reasonably accessible to the patient (e.g., is covered by the patient's insurance or wouldn't otherwise create a financial hardship for the patient).
- *The* data suggest that the study drug is not effective for postmenopausal women with ER+ advanced breast cancer.
- The Sponsor has reasonable safety concerns regarding the study drug as treatment for postmenopausal women with ER+ advanced breast cancer.
- Provision of study drug is not permitted under the laws and regulations of the patient's country.

Genentech does not intend to provide other study interventions to patients after the conclusion of the study or any earlier withdrawal.

The Roche Global Policy on Continued Access to Investigational Medicinal Product is available at the following Web site:

[http://www.roche.com/policy\\_continued\\_access\\_to\\_investigational\\_medicines.pdf](http://www.roche.com/policy_continued_access_to_investigational_medicines.pdf)

## **10.6 MEASURES OF TREATMENT COMPLIANCE**

At each clinic visit starting with Cycle 2, patients will be asked to return any remaining applicable study drug GDC-0810 and/or study drug treatment (i.e. palbociclib) from the previous dosing cycle as well as all used and unused study drug containers.

In the dose escalation portion of the study, patients should also bring their study drug containers to the weekly visits in Cycle 1 in order to verify treatment compliance for the DLT evaluation period.

Treatment compliance will be defined as the number of tablets or capsules taken divided by the expected number of tablets and reported as percentage. In case of dose reductions, the expected number of tablets or capsules should reflect the new dose level.

Tablets or capsules that are not returned will be considered to have been taken, unless otherwise specified in the patient's CRF.

## **11. STUDY PROCEDURES AND GUIDELINES**

Schedule of Activities representing the required testing procedures to be performed during the study are diagrammed in [Appendix 1](#) (Phase Ia), [Appendix 2](#) (Phase IIa), [Appendix 3](#) (Phase Ib Cohort C1), and [Appendix 4](#) (Phase Ib Cohort D1).

Prior to conducting any study-related activities, written informed consent and any other authorizations must be signed and dated by the patient.

Every effort should be made to ensure that the protocol-required tests and procedures are completed as described. However, it is anticipated that from time to time there may be circumstances outside of the control of the investigator that may make it unfeasible to perform the test. In those cases, the investigator should take all steps necessary to ensure the safety and wellbeing of the patient. When a protocol-required test cannot be performed, the investigator will document the reason for this and any corrective and preventive actions which he/she has taken to ensure that normal processes are adhered to as soon as possible. The Sponsor study team should be informed of these incidents in a timely fashion.

### **11.1 CLINICAL ASSESSMENTS**

#### **11.1.1 Demographics**

Demographic information (e.g., date of birth and race) will be recorded at screening.

#### **11.1.2 Medical History**

Relevant medical history includes clinically significant diseases; smoking history, use of alcohol and drugs of abuse, history of current disease, surgeries, other pertinent clinical conditions, and information regarding underlying diseases will be recorded at screening.

All medications used by the patient within 7 days before the screening visit (e.g., prescription drugs, over-the-counter drugs, herbal or homeopathic remedies, nutritional supplements) will be recorded at screening.

### **11.1.3 Physical Examination**

A complete physical examination will be performed by either the investigator or a sub-investigator at screening. Qualified staff (e.g., nurses or physician assistants) may complete the abbreviated physical exam at all other visits. New abnormal physical exam findings must be documented and followed by a physician or other qualified staff at the next scheduled visit.

The physical examination should include, but is not limited to, general appearance, skin, neck, eyes, ears, nose, throat, breast, lungs, heart, abdomen, back, lymph nodes, extremities, and nervous system, as well as examination of known and suspected sites of disease. Height will be recorded at screening only.

### **11.1.4 Vital Signs**

Body temperature, blood pressure, pulse and respirations will be performed at screening and at every clinic visit.

### **11.1.5 Performance Status**

The ECOG performance status scale will be assessed at screening and at every clinic visit ([Appendix 6](#)).

### **11.1.6 Adverse Events**

Assessment of adverse events will include type, incidence, severity (graded by the NCI CTCAE, Version 4.0, [Appendix 7](#)), timing, seriousness, and relatedness. Adverse events will be assessed at every clinic visit.

### **11.1.7 Concomitant Medications and Treatments**

All concomitant medication and concurrent therapies will be documented at screening and at every clinic visit. The indication for administration and dates of medication will be captured.

### **11.1.8 Tumor Assessments**

Disease assessments will be performed at screening, *per institutional guidelines, and as clinically indicated*.

Imaging studies will include a CT scan of the chest, abdomen, and pelvis, plus a bone scan. At screening, a CT/MRI brain should be obtained if clinically indicated to rule out newly diagnosed, untreated brain metastasis.

Radiographic confirmation of objective tumor response or disease progression will be based on RECIST v1.1 ([Eisenhauer et al. 2009](#)).

The same method of assessment and the same technique should be used at screening and during follow up. Intravenous (IV) contrast is required when not medically contraindicated. Patients who have a contraindication to IV contrast may have MRI exams of the abdomen and pelvis performed in lieu of CTs and a non-contrast CT of the chest. Tumor evaluation by PET scan or by ultrasound may not substitute for CT or MRI scans. However, a CT for tumor assessment may be acquired on a PET/CT scanner if it is of full diagnostic quality and includes IV contrast.

### **11.1.9 Endometrial Thickness Assessments (if applicable)**

*To assess for any potential effect of *study treatment* on the uterus, transvaginal ultrasound scans will be performed to monitor endometrial thickness *at screening, the study drug discontinuation visit, and as clinically indicated*. Transvaginal ultrasounds are not required for patients who have had a hysterectomy.*

## **11.2 CLINICAL LABORATORY MEASUREMENTS**

Blood and urine will be obtained *as clinically indicated (except creatinine and liver function tests)* and analyzed at a local or central laboratory for hematology, blood chemistry profile, and urinalysis, respectively. *Liver function test and creatinine will be collected at least monthly and as clinically indicated.* [Appendix 5](#) lists all of the specific tests that will be performed.

Investigators may have additional local laboratory tests performed for the purpose of planning treatment administration, dose modification, or following adverse events.

### **11.3 ELECTROCARDIOGRAM (ECG)**

#### **11.3.1 Phase Ia**

Standard single 12-lead ECGs (with a 10-second rhythm strip) will be collected at screening and at Cycle 2 Day 1 at the 2-hour post-dose timepoint (prior to the respective PK sample collection). ECGs should be collected after the patient has rested quietly and is awake in a fully supine (or semi-recumbent, if supine is not tolerated) position for 5 to 10 minutes and prior to any blood draw collection.

#### **11.3.2 Phase IIa**

During Phase IIa, all patients will participate in the evaluation of the effect of GDC-0810 on ventricular repolarization. Triplicate 12-lead ECGs (with a 10-second rhythm strip) will be collected approximately 2 minutes apart at screening, at Cycle 2 Day 1 predose, and at 1, 2, 3, 4, and 6 hours following dosing.

After each set of ECGs on Cycle 2 Day 1, blood samples to assess PK will be collected (see Section [11.4.2](#)).

ECGs will be recorded and evaluated at the clinical study (local) site for the purposes of real-time cardiac safety monitoring for individual patients and will be subsequently

analyzed at a designated central facility for the purposes of assessing the effects of GDC-0810 on the QTc and other cardiac intervals. For real-time safety monitoring of patients, only one ECG printout per timepoint (of the triplicate samples) will need to be reviewed by the investigator. For the purposes of central analysis, triplicate ECGs will be obtained in a rigorous and standardized fashion and transmitted digitally to the central reading facility for review and interpretation by specialized cardiac readers.

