## 1.2 CLINICAL PK SUMMARY

The clinical pharmacokinetics of GDC-0810 is under investigation in the ongoing clinical Phase Ia/Ila Study GO29642. Preliminary PK information from this study is summarized below.

- GDC-0810 was rapidly absorbed with peak concentrations achieved at 1–3 hours after dosing.
- The mean terminal half-life was approximately 8 hours, and mean apparent oral clearance was 8 L/hour after a single dose of GDC-0810 at 600 mg under the non-fasted condition. Consistent with the half-life, minimal drug accumulation was observed following multiple dosing.
- GDC-0810 exposure in the fasted state increased with dose across the entire dose range tested (100–800 mg).
- In the Phase Ia *portion of the study*, at 600 mg QD, mean $\pm$ SD steady state  $AUC_{0-6}$  and  $C_{max}$  for GDC-0810 was  $41.1 \pm 27.5 \mu\text{g} \cdot \text{hour/mL}$  and  $11.8 \pm 6.61 \mu\text{g/mL}$ , respectively, under the fasted state (n=6), and  $74.9 \pm 30.1 \mu\text{g} \cdot \text{hour/mL}$  and  $25 \pm 8.35 \mu\text{g/mL}$ , respectively, under the nonfasted state (n=5).
- In the Phase Ila *portion of the study*, at the RP2D of 600 mg QD under the fed state, mean $\pm$ SD steady state  $AUC_{0-6}$  and  $C_{max}$  for GDC-0810 was  $39.5 \pm 22.5 \mu\text{g} \cdot \text{hour/mL}$  (n=40) and  $14.3 \pm 7.3 \mu\text{g/mL}$  (n=42), respectively.

Based on pharmacodynamic (PD), clinical tolerability, and preliminary PK data collected to date, once-daily administration of 600 mg under fed conditions (within 30 minutes after eating a meal) was selected as the single-agent RP2D for GDC-0810. See the GDC-0810 Investigator Brochure for further details.

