#### Phase IIa

- To evaluate the safety of GDC-0810 single agent when administered at the RP2Ds in women with locally advanced or metastatic ER+ (HER2-) breast cancer
- To evaluate the effect of GDC-0810 single agent on ventricular repolarization in postmenopausal women participating in the Phase IIa portion of the study

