### **11.4.2 Phase IIa**

Blood samples for determining trough PK (predose) concentrations of GDC-0810 will be collected in Cycles 1, 2, 3 and 4.

Additionally, on Cycle 2 Day 1, PK samples will also be collected predose and at 1, 2, 3, 4, 6 hours following dosing. If PK sampling times coincide with ECG collection times, the ECGs have to be assessed prior to PK blood collection.

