### **15.3.6 Ventricular Repolarization**

Standard ECG intervals RR and QT will be determined for each ECG recording. Corrected QT intervals (QTc) will be determined using Fridericia's formula. Changes in ECG intervals from baseline will be calculated. Baseline is defined as either the single ECG measurement (Phase I) or the mean of the triplicate ECG measurements (Phase II) collected during screening. Standard evaluation procedures will be employed in the reading of the ECGs.

Tables to be prepared include analysis of time-matched mean differences between baseline and postdose assessments, and analysis of maximum change from baseline for each patient.

In addition, patient's QTc (Fridericia) will be categorized based on ICH E14 guidance. Tables will present the number and percentage of patients meeting or exceeding the following categories:

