### **15.4 PHARMACOKINETIC ANALYSES**

For PK analyses, the analysis population will consist of the subset of treated patients who have at least one PK sample collected.

During the Phase Ia *portion of the study*, full plasma PK profiles will be obtained for GDC-0810 and its glucuronide metabolites, and analyzed using non-compartmental methods for all patients in the dose escalation portion of the study.

In the Phase IIa portion of the study, full plasma PK profiles will be obtained for GDC-0810 and analyzed using non-compartmental methods.

In the Phase Ib portion of the study, full plasma PK profiles will be obtained for GDC-0810 and palbociclib and/or LHRH agonists and analyzed using non-compartmental methods.

In addition, in the Phase Ia/IIa/Ib, blood samples for determination of the steady-state trough concentrations (predose) of GDC-0810 will be *obtained from* all patients.

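### Phase IIa pairs triplicate ECGs with drug concentrations at six Cycle 2 Day 1 times, but no planned analysis relates QTcF to concentration

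*Combined protocol and SAP*

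**What the plan says.** All references are to the combined protocol and SAP.

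- **Objective.** Section 6.2 lists as a Phase IIa secondary objective: "To evaluate the effect of GDC-0810 single agent on ventricular repolarization in postmenopausal women participating in the Phase IIa portion of the study".
- **ECGs.** Section 11.3.2 schedules triplicate ECGs "at screening, at Cycle 2 Day 1 predose, and at 1, 2, 3, 4, and 6 hours following dosing".
- **PK.** Section 11.4.2 gives the same times for Cycle 2 Day 1: "PK samples will also be collected predose and at 1, 2, 3, 4, 6 hours following dosing". Section 11.3.2 fixes the order: "After each set of ECGs on Cycle 2 Day 1, blood samples to assess PK will be collected". Appendix 2, footnote 10, also treats the ECGs as matched to PK samples.
- **QTc analysis.** Section 15.3.6 says "Changes in ECG intervals from baseline will be calculated", with the screening triplicate mean as the Phase IIa baseline. It continues: "Tables to be prepared include analysis of time-matched mean differences between baseline and postdose assessments, and analysis of maximum change from baseline", the latter per patient. It then adds counts of patients by absolute QTcF and by increase from baseline.
- **PK analysis.** Section 15.4: "In the Phase IIa portion of the study, full plasma PK profiles will be obtained for GDC-0810 and analyzed using non-compartmental methods".
- **Elsewhere.** Section 15.1 (planned analyses) and Section 15.6 (exploratory studies) add no exposure-QTc analysis.

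**The concern.** The schedule has the structure that a concentration-QTc analysis needs: replicate ECGs, a concentration drawn straight after each set, and a range from trough to peak within each patient. The analysis sections then treat the two data streams separately.

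This matters because exposure at one dose varies widely in the plan's own figures. A mean change at a fixed clock time is an average over whatever concentrations the patients had at that time. If QTcF rises with concentration, that mean reflects average exposure and cannot say what to expect at higher concentrations seen at the same dose. As a hypothetical illustration, under a straight line through zero, a 10 msec effect at 25 µg/mL would appear as 10 × 14.3/25 = 5.7 msec at 14.3 µg/mL.

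Section 10.4.1 also permits interruptions and reductions during Phase IIa, so some patients may reach Cycle 2 Day 1 below 600 mg. The documents do not say how many. The by-time table would average them in, whereas a model on measured concentration uses the exposure each patient actually had.

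**Working it through.** The plan states no margin, power or precision for the QTc objective, so there is no design figure to reproduce. The checks below use the steady-state Cmax values in Section 1.2, which that section calls preliminary.

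| Group, 600 mg QD | Mean Cmax (µg/mL) | SD | n |
|---|---|---|---|
| Phase IIa, fed | 14.3 | 7.3 | 42 |
| Phase Ia, nonfasted | 25 | 8.35 | 5 |
| Phase Ia, fasted | 11.8 | 6.61 | 6 |

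**1. Is the pairing used?** ECG and PK times on Cycle 2 Day 1 are both predose, 1, 2, 3, 4 and 6 hours, which is six pairs per patient. That gives up to 6 × 100 = 600 pairs for the planned cohort, or 6 × 42 = 252 for the patients with Cmax in Section 1.2. None of the outputs in Sections 15.1, 15.3.6, 15.4 or 15.6 contains both QTcF and concentration.

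**2. Where does average Phase IIa exposure sit?**
- Against Phase Ia nonfasted: 1 − 14.3/25 = 42.8% lower.
- Against Phase Ia fasted: 14.3/11.8 − 1 = 21% higher.
- For AUC over 0 to 6 hours, 1 − 39.5/74.9 = 47% lower than nonfasted and 1 − 39.5/41.1 = 4% lower than fasted.

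The mean concentration at any one sampling time cannot exceed the mean of the individual maxima, so 14.3 µg/mL is an upper bound for the exposure behind a by-time mean in these patients.

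**3. How firm is the 43%?**
- 95% CI for the nonfasted Phase Ia mean: 25 ± 2.776 × 8.35/√5 = 14.6 to 35.4 µg/mL.
- With 14.3 held fixed, the shortfall runs from 1 − 14.3/14.63 = 2% to 1 − 14.3/35.37 = 60%.
- Welch comparison: difference 10.7, SE = √(8.35²/5 + 7.3²/42) = 3.90, t = 2.74 on 4.8 df, p = 0.043, 95% CI 0.5 to 20.9 µg/mL.

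**4. Is 25 µg/mL within the Phase IIa range?** The documents give only mean and SD, so a shape must be assumed.
- Normal: z = (25 − 14.3)/7.3 = 1.47, so P(Cmax > 25) = 7.1%.
- Log-normal, moments matched: σ² = ln(1 + (7.3/14.3)²) = 0.232, σ = 0.481, μ = ln 14.3 − 0.116 = 2.544. Then z = (ln 25 − 2.544)/0.481 = 1.40, so P = 8.1%.

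That is about 3 of 42 patients, or 7 to 8 of 100. The 95th percentile is 26.3 (normal) or 28.1 (log-normal) µg/mL. A prediction at 25 µg/mL would lie in the upper tail of the expected range, supported by few patients.

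**5. What would each table show?** The by-time table compares every Cycle 2 Day 1 time with one screening value and does not use the trough-to-peak contrast within a patient. The maximum-change and category tables count each patient at her own exposure but do not report it, so a QTcF rise with concentration could not be seen in them.

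**The case against.** The strongest case against is that the objective is already answered. It asks about the women in Phase IIa, and mean change in those women, at the exposure they actually have, addresses it. The maximum-change and category tables go further and include the high-exposure patients. Section 15.3.6 also defines a baseline for Phase I ECGs. Phase Ia patients have a single ECG 2 hours after the Cycle 2 Day 1 dose (Section 11.3.1), within the 1 to 3 hour peak window of Section 1.2, at doses up to 800 mg. The study is exploratory, the list of tables in Section 15.3.6 is not worded as exhaustive, enrolment is closed and development has been halted for reasons stated to be unrelated to safety.

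Most of this stands, and it limits the point. A reader might infer that QTc is judged only at low exposure. The documents do not support that, because individual tables and Phase Ia ECGs exist and some Phase IIa patients would be expected above 25 µg/mL. A reader might also take 43% as an established shortfall. It rests on five patients, and the fasted comparison goes the other way, although nonfasted is the closer match to Phase IIa dosing.

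A further objection concerns the remedy. There is no placebo arm and only one screening baseline, so a model's intercept and time terms would absorb drift since screening and diurnal change. This also stands. It is a reason not to make the model the main analysis. The slope still draws on concentration contrasts that none of the planned tables uses. The Phase Ia ECGs do not fill the gap: they are single recordings at one postdose time, and Section 15.1 summarises data by phase and dose cohort.

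**Conclusion.** The gap is real and modest. Paired ECG and concentration data are collected for a named secondary objective, and no stated analysis relates the two. The by-time mean therefore speaks to average Phase IIa exposure only: mean Cmax 14.3 µg/mL, 43% below five nonfasted Phase Ia patients (about 2% to 60%) and 21% above six fasted ones. The other two tables reach higher exposures but cannot relate QTcF to them.

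This rests on the preliminary Cmax summaries in Section 1.2 and, for the share above 25 µg/mL, on an assumed normal or log-normal shape. The need for the model does not depend on the exact 43%. Nothing in the documents shows that a QTc effect exists or has been missed, or that the planned tables should be replaced. Label: cheap improvement.

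**What to change.** Add to Section 15.3.6, alongside the planned tables, a linear mixed-effects model on the Phase IIa Cycle 2 Day 1 pairs:

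change in QTcF = intercept + slope × concentration + centred baseline QTcF + nominal time (categorical), with a random intercept and random slope per patient.

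Report:
- the slope with a two-sided 90% CI;
- the predicted change with a two-sided 90% CI at 14.3 and 25 µg/mL, at one nominal time named in advance. The difference between the two predictions is (25 − 14.3) × slope = 10.7 × slope, which is free of the intercept and time terms;
- a sensitivity analysis that pools the Phase Ia 2-hour pairs, noting that these are single ECGs.

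State the limits in the same paragraph: no placebo arm and a single screening baseline, so the slope is the interpretable quantity; and few patients inform the prediction at 25 µg/mL. This is estimation, so it fits the statement in Section 15.1 that no confirmatory inference is planned.

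The cost is one paragraph and one model, with no extra ECGs or samples.
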